6.1 Case number estimation

For the case number estimation for the primary endpoint the following assumptions are made:

Sensitivity:

Lindner et al. (in press) collected samples from the anterior nose and observed 27 of 29 SARS-CoV-2 PCR-positive samples ($> 10^6$ copies/mL) to also be rapid antigen test-positive (93.1% agreement). The case number estimation for the Dräger Antigen Test SARS-CoV-2 is based on a more conservative expectation of 90% sensitivity. This assumption is based on preliminary performance data of the test under evaluation and the threshold for PCR set to 10^6 copies/mL (refer to 6.2 for details).

The half width of the confidence interval (W) is pre-determined at 5%, as $90\% \pm 5\%$ provides sufficient test reliability for a daily application in the clinical setting. A test sensitivity of 85% would still meet the PEI criterion for antigen tests (sensitivity $> 80\%$; PEI, 2021).

Specificity:

Lindner et al. (in press) observed a rapid antigen test specificity of 99.6% (95% CL, CI 97.8-100.0%) in anterior nasal swabs. As a result, the investigational product is expected to be 99% specific. For diagnostic applications, a device should deliver a specificity of 99% with a precision of $\pm 1\%$ in order to be of service, e.g. in the screening of symptomatic patient at times of high incidence. It also needs to be taken into account that the intended use of the investigational product is for screening; ultimate confirmation of the preliminary result remains for more sensitive PCR testing.

Separate calculations for case numbers for sensitivity and specificity of the test are performed following the approach by Hajian-Tilaki (2014). The following formulae are used:

$$N(SN) = z^2 \times \frac{(SN(1 - SN))}{W^2 \times P}$$
$$N(SP) = z^2 \times \frac{(SP(1 - SP))}{W^2 \times (1 - P)}$$

with

- N = Case Number
- SN = Sensitivity
- SP = Specificity
- z = z-value corresponding to a confidence level of 95%
- P = Prevalence of disease in the test population. Prevalence is assumed to be at least 20% based on current data from the prospective study sites indicating an actual prevalence among all participants tested for SARS-CoV-2 of 25%.
- W = maximum marginal error (half width of 95% confidence interval) for sensitivity and specificity, respectively

The resulting case number estimation for sensitivity evaluation of the investigational product is 691. Assuming a 5% dropout rate, 726 participants have to be enrolled. For specificity evaluation, 500 participants (allowing for up to 5% dropouts) need to be enrolled. Since the prevalence of PCR-negative participants is assumed to be at 80%, more test negative cases (580) are expected to be enrolled in the study for the determination of sensitivity alone. As a

result, the cases needed for specificity assessment are covered by the case number estimated for sensitivity assessment. In explicit, 726 participants are enrolled to sufficiently power overall sensitivity and specificity evaluation of the test product.

Based on the current testing strategy (Federal Ministry of Health, Germany, Dec. 16, 2020) and according to communications with the study site (Dec. 2020), more symptomatic than asymptomatic persons present themselves for PCR testing at the site. In order to ensure a minimum of 100 asymptomatic cases to be included in the performance evaluation of the investigational product (PEI, 2021), an additional 105 participants are added to the total case number. This allows for a 5% dropout rate among asymptomatic participants, and it ensures performance evaluation of the test for asymptomatic people even if most or all cases enrolled for overall sensitivity and specificity evaluation belong to the symptomatic group.

As a result, the total case number estimate for this study adds up to $726 + 105 = 831$.

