6.3 Assessment of primary objective

Dräger test and PCR results for all participants are recorded. All valid data pairs (valid Dräger test result, valid PCR result, complete records as defined on pp. 13) from the symptomatic group feed into sensitivity and specificity evaluation of the Dräger test. A contingency table is used to present sensitivity, specificity, and associated confidence intervals (CI at a confidence level of 95%).

Table 7. Assessment of results.

Dräger Antigen Test SARS-CoV-2 result	Reference method RT-PCR result	
	Positive	Negative
Positive	True positive (TP)	False positive (FP)
Negative	False negative (FN)	True negative (TN)

Key parameters to be determined:

$$\text{Sensitivity} = \frac{\text{TP}}{\text{TP} + \text{FN}} \times 100$$

$$\text{Specificity} = \frac{\text{TN}}{\text{FP} + \text{TN}} \times 100$$

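### Does leaving the symptom status of the 726 participants unstated in section 6.1 put the primary precision targets at risk?

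*Combined protocol and SAP*

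**What the plan says.** The synopsis and section 3.1 define the primary objective in symptomatic people. Section 6.3 carries this through: only valid pairs "from the symptomatic group feed into sensitivity and specificity evaluation of the Dräger test".

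Section 6.1 opens its calculation with "For the case number estimation for the primary endpoint the following assumptions are made". It takes 90% sensitivity with a half-width of 5 points, and states that "a device should deliver a specificity of 99% with a precision of" ±1%. The planning prevalence is at least 20%, backed by site data "indicating an actual prevalence among all participants tested for SARS-CoV-2 of 25" per cent. The result is that "726 participants are enrolled to sufficiently power overall sensitivity and specificity evaluation of the test product". Their symptom status is not given.

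On the mix, section 6.1 says only that "more symptomatic than asymptomatic persons present themselves for PCR testing at the site". It then adds 105 people, with the purpose "In order to ensure a minimum of 100 asymptomatic cases to be included in the performance evaluation", so that this group is covered "even if most or all cases enrolled for overall sensitivity and specificity evaluation belong to the symptomatic group". The total is 831, rounded up to about 850 in the synopsis and section 2.

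**The concern.** Any asymptomatic person counted among the 726 adds nothing to the primary analysis. The asymptomatic group has a stated minimum and no maximum; the symptomatic group has no stated number. The half-way point is triggered by 425 pairs of any kind. So enrolment of about 850 could finish, exactly as written, with fewer evaluable symptomatic participants than the ±5% and ±1% require. At stake would be wider intervals on the two headline estimates of the study.

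**Working it through.** **Inputs** (section 6.1 unless noted): sensitivity 0.90 with W = 0.05; specificity 0.99 with W = 0.01; z = 1.96; P = 0.20; 5% dropout; total about 850 (synopsis, section 2). The symptomatic shares and asymptomatic prevalences below are assumptions, because the documents give neither.

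**1. The plan's own figures.**
- Sensitivity: 1.96² × 0.90 × 0.10 / (0.05² × 0.20) = 691.5 (stated 691); 691 × 1.05 = 725.6, so 726.
- Specificity: 1.96² × 0.99 × 0.01 / (0.01² × 0.80) = 475.4; × 1.05 = 499.2, so 500.
- 726 + 105 = 831.

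All reproduce. In terms of counts, the targets need 691.5 × 0.20 = 138.3 reference-positives and 475.4 × 0.80 = 380.3 reference-negatives.

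**2. The natural reading: 726 symptomatic plus 105 asymptomatic.** Evaluable symptomatic: 726 × 0.95 = 689.7. At 20% prevalence this gives 137.9 positives and 551.8 negatives.
- Sensitivity: 1.96 × √(0.09/137.9) = ±5.01%.
- Specificity: 1.96 × √(0.0099/551.8) = ±0.83%.

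Both targets are met to rounding.

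**3. Other mixes.** Let s be the symptomatic share of 850, P the overall prevalence and Pa the asymptomatic prevalence. Symptomatic prevalence is then Ps = (P − (1 − s)Pa)/s. Evaluable positives are 850 × s × 0.95 × Ps, and negatives are 850 × s × 0.95 × (1 − Ps). Half-widths in percentage points, sensitivity / specificity:

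| P | Pa | s = 80% | 70% | 60% | 51% |
|---|---|---|---|---|---|
| 20% | 5% | 4.75 / 0.88 | 4.81 / 0.96 | 4.88 / 1.06 | 4.94 / 1.19 |
| 20% | 10% | 4.88 / 0.87 | 5.02 / 0.94 | 5.17 / 1.03 | 5.32 / 1.15 |
| 20% | 15% | 5.02 / 0.86 | 5.26 / 0.93 | 5.53 / 1.01 | 5.82 / 1.11 |
| 25% | 5% | 4.22 / 0.92 | 4.27 / 1.01 | 4.31 / 1.13 | 4.36 / 1.29 |
| 25% | 10% | 4.31 / 0.91 | 4.41 / 0.99 | 4.52 / 1.10 | 4.62 / 1.23 |
| 25% | 15% | 4.41 / 0.90 | 4.57 / 0.98 | 4.75 / 1.07 | 4.93 / 1.19 |

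Example (P = 20%, Pa = 15%, s = 51%): Ps = (0.20 − 0.49 × 0.15)/0.51 = 0.248; 850 × 0.51 × 0.95 = 411.8 evaluable; 102.1 positives and 309.7 negatives; ±5.82 and ±1.11.

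Fewer symptomatic participants usually means a higher positive rate among those who remain, which cushions sensitivity and moves the loss towards specificity. Sensitivity misses only at P = 20% with Pa of 10% or more.

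**4. Smallest symptomatic enrolment that meets both targets** (Pa = 5/10/15%): 556/606/688 at P = 20%, and 601/587/571 at P = 25%. All lie below 726.

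**5. Are the low shares plausible?** The added 105 are needed only if the 691 evaluable would hold fewer than 100 asymptomatic people, a share below 100/691 = 14.5%. At a symptomatic share of 51 to 60%, the 726 would already hold 726 × 0.40 = 290 to 726 × 0.49 = 356 asymptomatic people. The plan was guarding against too few asymptomatic participants.

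**6. Effect on the conclusion.** In the worst sensitivity cell, about 92 of 102 positives would be detected (90.2%). The exact (Clopper–Pearson) lower 95% limit is 82.7%, above the 80% minimum criterion that section 6.1 cites.

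**The case for a change.** The strongest reply is that a protocol should state the enrolment rule on which its sample size depends. The wording does allow asymptomatic people among the 726, and the only statement on mix would be satisfied by 51%. Specificity deserves particular notice, because section 6.1 itself ties the usefulness of the device to ±1%, and that target slips at a 60% share in every scenario above. The half-way review in section 7.4 covers enrolment and performance, but it has no symptomatic criterion.

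The textual point stands. What does not follow is that the study is undersized or will be misread. The 51% figure is the literal floor of a qualitative remark and not an expected mix. Symptoms and ct values are reported weekly and in the half-way report (section 4.5), the sponsor's board sees enrolment and performance at that point, and section 2 allows more testing after the half-way or end review. A cap on asymptomatic enrolment would also go beyond the need: 556 to 688 symptomatic participants suffice in these scenarios, and a cap would hold back a group that the synopsis sets at 100 or more.

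**Conclusion.** No change is needed. The calculation is correct, and read together with the symptomatic-only objective and the separate 105, it meets ±5% and ±1% to rounding. The unstated symptom status is missing detail that the site and analysts will fill sensibly. If the mix did drift to a 51 to 70% symptomatic share, the half-widths would reach at most about ±5.8% for sensitivity and ±1.3% for specificity. The estimates would stay valid, their intervals would be reported under section 6.3, and no planned test or decision rule depends on the width.

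This rests on assumed shares of 51 to 80% and asymptomatic prevalences of 5 to 15%, and on taking the 20% and 25% as prevalences at the 10⁶ copies/mL cut-off, which section 6.1 does not say. If symptomatic prevalence at that cut-off were 15%, ±5% would need 138.3/0.15/0.95 = 971 symptomatic participants, more than the whole study. That is a matter of the prevalence assumption, and stating the symptom status of the 726 would not alter it.

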6.2 RT-PCR, cycle thresholds and viral concentration

PCR as the gold standard for SARS-CoV-2 detection provides the benchmark for this performance evaluation study, i.e. a true representation of the actual SARS-CoV-2 state of the participant (positive or negative). Following RKI reasoning (RKI, 2020a), RT-PCR results are not only scored as absolute results of positive or negative, but also in the context of detected viral load per sample within the PCR positives. The RKI provides a threshold of 10^6 copies/mL beyond which the viral culturability potential seems neglectable (cell culture experiments as *in vitro* test to indicate infectiousness) (RKI, 2020b). Based on the PCR assay and cycler combination used for sample analysis, this viral concentration translates into a system-specific cycle threshold (ct) value for each sample, when the system is calibrated with reference standards (RKI, 2020a). This study uses the system-specific ct value corresponding to 10^6 RNA copies/mL to sort the PCR positives into either above or below this threshold.

Sensitivity and specificity of the Dräger test are determined based on true- and false-positive as well as true- and false-negative counts determined by comparing the Dräger test results to PCR results scored as follows:

- PCR-negative: negative PCR and positive PCR with viral concentration $< 10^6$ copies/mL, and
- PCR-positive: positive PCR with viral concentration $\geq 10^6$ copies/mL.

Based on RKI information (RKI, 2020a), this ct cut-off value is expected to be at approximately 30 cycles and is determined by the diagnostic laboratory analyzing the PCR samples for this study.

6.3 Assessment of primary objective

Dräger test and PCR results for all participants are recorded. All valid data pairs (valid Dräger test result, valid PCR result, complete records as defined on pp. 13) from the symptomatic group feed into sensitivity and specificity evaluation of the Dräger test. A contingency table is used to present sensitivity, specificity, and associated confidence intervals (CI at a confidence level of 95%).

Table 7. Assessment of results.

Dräger Antigen Test SARS-CoV-2 result	Reference method RT-PCR result	
	Positive	Negative
Positive	True positive (TP)	False positive (FP)
Negative	False negative (FN)	True negative (TN)

Key parameters to be determined:

$$\text{Sensitivity} = \frac{\text{TP}}{\text{TP} + \text{FN}} \times 100$$

$$\text{Specificity} = \frac{\text{TN}}{\text{FP} + \text{TN}} \times 100$$

6.4 Assessment of secondary objectives

Secondary endpoints are of explorative nature and descriptive statistics are used for evaluation (mean, median, minimum, maximum, frequencies, standard deviation, 95% CL confidence limits).

All valid data pairs (valid Dräger test result, valid PCR result, complete records) feed into sensitivity and specificity evaluation of the Dräger test. Sensitivity and specificity including lower and upper confidence limits for the test under evaluation are calculated for different cut-offs of the ct value of the PCR test in addition to the predefined ct value for the primary endpoint (currently defined by a viral concentration of 10^6 RNA copies/mL and to be calibrated to ct). Prerequisite for inclusion in this explorative evaluation is that the case record is not only complete as defined above, but also provides the information required to allow sorting into groups according to e.g. ct values.

Sensitivity and specificity including lower and upper confidence limits for the test under evaluation are calculated for participants grouped by

- ct value (as described above),
- time since symptoms onset (using the general cut-off ct value of the PCR test used for the primary endpoint evaluation; on symptomatic group only),
- symptom status (symptomatic vs asymptomatic).

In addition to sensitivity and specificity centric explorative evaluation, the frequency of lasting nosebleeds or unbearable pain in participants is tracked. The primary information is captured in the CRF. Once the 50 participants have been enrolled the fraction of participants reporting such experiences is determined daily.

7. DATA QUALITY ASSURANCE

7.1 Training of study staff

Staff receives hands-on training for the Dräger Antigen Test for SARS-CoV-2 prior to collecting study specimens. This training is documented on the Operator Training Form (see Appendices below).

Red-green visual impairments disqualify staff as operators for this trial.

7.2 Case Report Form (CRF)

For each participant enrolled in the study, a case report form collects all study-relevant information. The corresponding patient file is archived at the study site. These two records are linked only by participant ID, as the clear name of the patient is not recorded on the case report form.

The operator documents the respective steps of the procedure and other case information in the CRF. Operator and Principal Investigator confirm these records are complete. Corrections are made such that the original entry stays legible. The new entry is dated and signed, too.

7.3 Archiving/Record retention

Data generated are documented, recorded, reported and archived in conformity with the CPSP and national standards. Records (Investigator Site File and Trial Master File) are retained for at least 10 years after completion or suspension of the trial. The Sponsor keeps a part of the documentation relating to the trial for as long as the product is authorized.

7.4 Monitoring

Monitor

The Sponsor defines a representative as Monitor of the Study prior to study start. The Monitor is the primary contact for the clinical study site and all questions related to the study. In addition, the Monitor checks in with the site and may request information or documentation pertaining to the study as she/he sees fit (prior to and during the trial).

Selected original documentation and database entries are compared by the Sponsor as a cross-check.

Sponsor

The Sponsor receives regular updates from the site on study progress, adverse events and preliminary data. This information is used to determine the fraction of all participants reporting pain or/and nosebleed as a result of specimen collection (or the frequency of pain and nosebleeds). When reaching 50 enrolled participants, the counts are tracked daily using the PI's daily updates and any potential Adverse Event notifications. Should at any point of time > 10% of participants report unbearable pain or lasting nosebleed the study stops.

The Sponsor's Decision Board - in its role as the complaint handling entity for clinical studies - evaluates, e.g. every SAE that may occur during the study and defines next steps.

At half-way point of the study the Sponsor's Decision Board reviews an overview of study-related information, e.g. device performance, AE summary, enrollment. The goal is to evaluate overall study progress and current safety and performance status of the investigational product. The board may take the decision to interrupt the study or terminate it early. Refer to 5.3 for selected scenarios.

7.5 Audits

Audits can be scheduled as needed. Currently, no inspections are planned during the course of this study.

7.6 Privacy

Data collected during this study includes personal information. Patient-related information including the clear name is managed, stored and archived only at the study site. The Sponsor only receives study-relevant information as collected in the CRF (which is identified by participant ID, not the patient name, i.e. pseudonymized).

Only dedicated study staff enter into and access study data records, i.e. access is restricted to authorized personnel, all of which abide current legislation on privacy.

Should a study participant decide to retract from this study, any existing entries would be deleted. Any personal information associated with this study would be destroyed after up to ten years, unless defined otherwise by legal or in-house requirements.

8. ETHICS AND REGULATORY REQUIREMENTS

All parties involved in this trial execute the study according to applicable laws and regulations and under consideration of the WMA Declaration of Helsinki.

The Ethics Committee of the site reviews the study protocol and accompanying documents. Suggestions by the Ethics Committee are taken into account such that the study can be approved and conducted. The study cannot be conducted should the Ethics Committee disapprove of parts of or the whole study protocol. The committee is also informed about any safety issues that might occur during the study as well as the closing of the study.

9.2 Funding

The study is funded by Dräger.

10. PUBLICATION

A Clinical Performance Study Report summarizes the events and outcome of the study. Key results are included in the Instructions for Use to be provided to kit users upon purchase or request after product release. The PI may publish the outcome of this study as a scientific publication after product release. Details are addressed in a separate contract.

